randomization, to maximize the likelihood that treatment groups will be balanced with respect to demographic variables (presence of children from prior unions) and prognostic variables (frequency of IPV). We will use a Microsoft Access-based program previously developed for the Yale Department of Psychiatry NIDA-funded Psychotherapy Development Center and used in prior studies by Co-PI [name]. In urn randomization, an algorithm modifies ongoing randomization probabilities based on prior composition of treatment groups, and maximizes multivariate equivalence of treatment groups (Stout et al., 1994). Thus, urn randomization offers the benefits of balancing allocation of important prognostic variables in treatment groups, while still retaining other benefits of random assignment (Wei, 1978).

Once enrolled, parents assigned to the treatment group are contacted by the Intake Coordinator or Resource and Referral Navigator who introduces their mentors and delivers the participants' gift cards for completing the intake assessment. Mentors arrange two initial 1-on-1 mentorship sessions with the parents, as per the FIOC protocol, after which the FIOC intervention commences. Families randomized to the control group are contacted by the Intake Coordinator or Resource and Referral Navigator, who schedules a meeting to deliver gift cards for completing the intake assessment. The R&R Navigator also provides a listing of existing Pinellas County Services and offers parents the opportunity to contact her at any time for assistance with referrals to Pinellas County services for pregnant or parenting families. All families, regardless of assignment, are also reminded about the follow-up assessments that will be completed at 3 months post-partum; and at 12 months post-partum. A formal check-in will be completed at 1-month post-partum (Congratulations on the birth card sent), and episodic newsletters and reminder texts (for families consented after January 30, 2017) will be sent at staged intervals to help keep in touch. Texts or phone calls to keep in touch will be sent to female participants by female staff only to ensure comfort of research participants.

All study participants will be offered the opportunity to be seen for initial assessments, follow-ups and mentoring sessions in person or via the Microsoft Teams platform.

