Child Outcome Measures at Time 3: An adapted version of the Infant Toddler Social Emotional Assessment (ITSEA; Carter & Briggs-Gowan, 2006), comprised of the full Brief Infant Toddler Social Emotional Assessment (BITSEA) and select additional scale items from the longer ITSEA instrument, was developed in consultation with the scale’s author. The instrument measures both social-emotional/ behavioral problems and delays in competency for children ages 12-36 months. It is a 71-item parent-report index constituting of six sub-scales: Problem behavior, competence, compliance, negative emotionality, aggression, and sleep.

5. Sample size justification:

We employed a computer program provided by Murphy et al. (2009; the same information is available from the tables in Cohen, 1988) to compute the significance level required for a projected sample size, incorporating attrition estimates, of $N=120$ (60 each in the treatment and control groups, respectively). Assuming the null effect hypothesis and alpha set at .05 and power of .8, an $F(1, 117)$ of 7.74 with a $d = .514$ is required for significance. Keeping the null hypothesis test, alpha .05 and lowering power to .5, an $F(1, 117) = 4.03$ with a $d = .37$ is required for significance. Drawing on effect size estimates from the feasibility study, even with low power (.5) resulting in a $d=.37$ we would be positioned to establish the effect of the FIOC treatment for 10 of the 12 FIOC variables (10 of the 12 SCID-evaluated couple problem-solving and communication variables summarized earlier had a d greater than .33).

6. Sample type or inclusion and exclusion criteria for participating in the research:

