Exclusion Criteria: Families will be excluded if they: 1) demonstrate evidence of psychotic symptoms or suicidal ideation on the Brief Symptom Inventory; 2) either partner has recently (over the past 12 months) been arrested and convicted for violence (assault) perpetrated against someone other than a current or former partner who is the co-parent of one of their children; or 3) are deemed high risk or in need of more intensive intervention. Risk determination is made by weighing the parent's report on the Danger Assessment Scale (DAS). As a rule of thumb, a DAS score of 9 or higher will result in automatic exclusion from the study. However, it is also possible that even with a score below 9, the parent may disclose one or more of the following issues during administration of the DAS, any of which would result in exclusion from the study: 1) parent reports she has required medical care because of significant injuries due to his violence, 2) parent says she fears for her life, 3) parent reports that the partner has threatened with a weapon and owns a gun or has a gun in the household; 4) parent reports that the partner has threatened to kill her; 5) parent reports that violence has escalated recently; 6) parent reports the partner's use of illicit drugs such as cocaine, methamphetamines, hallucinogens, or opiates .

7. Expected results of the research (reports, materials, discussion papers, contributions to theory):

Results will equip the research team with answers to study objectives and determine whether there would be value in studying the curriculum in a future multi-site implementation trial.

8. Study Staff

- 1. [name].**, P.I. Will provide all project oversight; serve as IRB officer; ensure research integrity and compliance; chair senior staff and other relevant team meetings; supervise fidelity-monitoring efforts; oversee proper implementation of all protocols, data collection, evaluation of videotaped infant and family data, data management and entry, analyses, report writing, and dissemination of findings.

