Safety is our paramount concern. Any mother referred to the study who thought she would be in danger if she took part in a coparenting intervention with the father would not be recruited to the study, but instead would be referred to a community agency more properly situated to provide needed support services. The same is true if a family is assessed and reports a level of trauma beyond the capacity of the project to safely accommodate. If after a family has been randomized to the study, high levels of conflict without violence are reported or witnessed during the course of the intervention -- but the participating mother does not express concern that she is in danger -- the female Mentor has been trained to work with the mother to identify a "mother-specific" mechanism for checking back in with her later, after the individual session ends, to ascertain (in an ongoing way, if indicated) whether all remains well. For higher-conflict couples randomized to the intervention, gender-specific individual preparatory sessions (part of the usual individual Mentorship meetings completed individually with mothers and fathers following the intake

assessment and before the FIOC curriculum commences) addresses with the parent how violence is bad for both the parents and the baby. Parents are enjoined to form a plan for safe, supportive participation in coparenting. After the individual mentorship sessions parents and Mentors come together for FIOC session 1, and at the end of this session all four individuals sign a Project Agreement symbolizing their commitment to a safe and violence-free pregnancy..

Additional Staff Training Safeguards

In addition to the opportunity for weekly clinical supervision, project staff who work directly with the mothers and fathers) also are provided both initial and ongoing trainings and in-service workshops that regularly revisit work with pregnant women, safety issues, Intimate Partner Violence and procedures in handling high levels of depression and suicidality. These trainings are offered bi-annually or more frequently if needed.

Dissatisfaction Safeguards

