## **Cover Letter**

### **Statistical Analysis Plan**

**Document Date 1.31.2022**

**NCT03097991**

### **FIOC Statistical Analysis Plan**

- Initial descriptive summations and simple statistical tests will compare groups.

- Primary Aims 1-4: Effects of the intervention. To examine if coparenting and individual adjustment outcomes are superior for FIOC families than for control group families at 3- and 12-months post-partum two-sided independent sample t-test for equivalence will first be employed for single time point comparisons. We will test hypotheses further using linear or generalized linear models to control for potential confounding and account for imbalance between the two treatment conditions.
- For longitudinal outcomes that are continuous (measured at Baseline; 3; and 12 months post-partum) we will use repeated measures analysis of covariance (ANCOVA; Crowder & Hand, 1990) to detect if treatment and control groups perform differently at any time points. For longitudinal outcomes that are categorical, generalized linear model (GLM, McCullagh & Nelder, 1989) will be used for the same purpose. Repeated measures ANCOVA and GLM allow us to account for correlation between repeated measures and detect possible moderating/confounding between treatment effects and subject individual differences. Multiple comparison adjustment will be addressed in analyses. We will report significance under both regular (.05) and Bonferroni-adjusted alpha.
- Exploratory Aim 1: To examine whether extent of father engagement is associated with better infant socioemotional adjustment regression analyses will examine variance in infants' 12-month ITSEA Internalizing, Externalizing, Dysregulation and Competence scores explained by 3- and 12-month father engagement.
- Exploratory Aim 2: To examine whether FIOC prevents the emergence of IPV and help to prevent future IPV in couples where it was previously reported, we will first explore simple chi-square analysis to compare FIOC and TAU conditions on the binary variable of any instance of physical violence between partners reported on the CTS2 over the 12 months of follow-up. Next,

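### The SAP has no analysis allowing for variation between the Mentors who deliver FIOC; if that variation exists and the conclusion is to reach beyond these Mentors, the standard errors are too small

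*SAP*

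**What the plan says.** **Delivery.** Protocol section 4 says of the treatment arm: "Mentors arrange two initial 1-on-1 mentorship sessions with the parents". Section 13, under Disclosure of Domestic Violence, continues: "After the individual mentorship sessions parents and Mentors come together for FIOC session 1, and at the end of this session all four individuals sign". The document signed is a joint agreement. Two parents and four signatories imply two Mentors per couple. Section 1 describes six prenatal sessions and a postnatal booster. Control families, per sections 1 and 4, get usual county services and a Resource and Referral Navigator, who also serves the FIOC arm. No Mentor sessions are described for them.

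**Analysis.** For Aims 1-4 the SAP starts with a "two-sided independent sample t-test for equivalence will first be employed for single time point comparisons". It goes on: "We will test hypotheses further using linear or generalized linear models to control for potential confounding" and to deal with imbalance between arms. For outcomes measured over time it says: "Repeated measures ANCOVA and GLM allow us to account for correlation between repeated measures". No test or model has a term for Mentor. On multiplicity it says: "We will report significance under both regular (.05) and Bonferroni-adjusted alpha".

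**Sample size.** Protocol section 5 uses 120 analysable families, 60 per arm, with no allowance for Mentor clustering.

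**Not stated anywhere.** The number of Mentors, families per Mentor, how Mentors are assigned, whether pairs are fixed, and any ICC.

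**The concern.** When several families in one arm are treated by the same people, their outcomes may share something of those people's skill and style. That is extra variation in the FIOC mean with no counterpart in the TAU mean. A test that treats families as independent leaves it out of the standard error and does not separate it from the treatment contrast.

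That FIOC families share Mentors is an inference, but a strong one. Assuming a near-equal split of the first 150 families, about 75 go to FIOC. Section 1 assigns up to 20 more (170 - 150) to FIOC, giving roughly 75-95. They are served in one county by one project team whose Mentors attend weekly supervision (section 13). One Mentor pair per family is not plausible.

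What is at stake is the decision in Protocol section 7: whether the curriculum merits a future multi-site implementation trial. Such a trial would use other Mentors, so for that purpose variation between Mentors belongs in the error term.

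**Working it through.** **1. The plan's own figure.** Inputs from Protocol section 5: 60 per arm, alpha .05, F(1,117) = 7.74, d = .514, power .80.
- d = 2 × √(F/117) = 2 × √(7.74/117) = .514, which matches.
- The critical F(1,117) is 3.92. Noncentral F power is .788 with noncentrality 7.74, and .797 with noncentrality 60 × .514²/2 = 7.93.
- For the second case (F = 4.03, d = .37, stated power .50) the same two routes give .512 and .520.

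The stated figures reproduce, and they do so with families treated as independent.

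**2. Mentor variation in the FIOC arm only.** Assumed, because the documents are silent: k equal Mentor pairs, m = 60/k families per pair, within-pair correlation ICC, total variance 1 in each arm.
- Design effect in FIOC: DE = 1 + (m - 1) × ICC
- Variance of the contrast: DE/60 + 1/60, against 2/60 if clustering is ignored
- Ratio of true to reported standard error: R = √((DE + 1)/2)
- Shortfall of the reported standard error: 1 - 1/R
- True two-sided error of the nominal .05 test: 2 × (1 - Φ(1.96/R))

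Example, 6 pairs and ICC .05: m = 10, DE = 1 + 9 × .05 = 1.45, R = √(2.45/2) = 1.107. The reported standard error is 1 - 1/1.107 = about 10% too small, and the true error is 2 × (1 - Φ(1.771)) = .077.

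| Pairs | ICC | DE | R | Reported SE too small by | True alpha |
|---|---|---|---|---|---|
| any | 0 | 1.00 | 1.000 | 0% | .050 |
| 8 | .01 | 1.065 | 1.016 | 2% | .054 |
| 8 | .02 | 1.13 | 1.032 | 3% | .058 |
| 8 | .10 | 1.65 | 1.151 | 13% | .089 |
| 6 | .05 | 1.45 | 1.107 | 10% | .077 |
| 4 | .05 | 1.70 | 1.162 | 14% | .092 |
| 3 | .01 | 1.19 | 1.046 | 4% | .061 |
| 3 | .02 | 1.38 | 1.091 | 8% | .072 |
| 3 | .10 | 2.90 | 1.396 | 28% | .160 |

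Simulation with no treatment effect (20,000 trials per setting) agrees: .058 for 8 pairs at ICC .02, .079 for 6 pairs at .05, .090 for 4 pairs at .05, and .156 for 3 pairs at .10.

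**3. Bonferroni does not remove it.** With 6 pairs and ICC .05, a test at an illustrative adjusted level of .005 has true level 2 × (1 - Φ(2.807/1.107)) = about .011.

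**4. Power at d = .514 once the variance is counted** (normal approximation, planned .80): .72 with 6 pairs and ICC .05, and .68 with 4 pairs and ICC .05. Satterthwaite degrees of freedom lower the 4-pair figure to .56.

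**The case against.** **The target of inference.** If FIOC did nothing for any family, whoever the Mentor, Mentors would not affect outcomes and this mechanism would not inflate the t-test. The 6-16% refers to a different null: zero average effect over a population of Mentors, of whom these are a sample. This stands. A reader might infer that Mentor differences are being counted as treatment effect, or that the estimate is biased. The documents do not support that: the average effect as delivered by these Mentors is not biased by clustering. The objection does not dispose of the point, because section 7 looks ahead to wider use and the SAP nowhere limits its inference to these Mentors.

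**Undocumented inputs.** Mentor numbers, pairing and ICC are all assumed. Supervision and training (section 13), and a principal investigator who is to "supervise fidelity-monitoring efforts" (section 8), may keep Mentor differences small. This also stands: it is why the size is given as a range that includes no effect. It would be too strong to say flatly that the error bars are too narrow or that families share fixed pairs.

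**TAU contact with Mentors.** Section 13, on monitoring recruitment and retention, has the Navigator and mentors contacting all families. A reader might infer that TAU families have no Mentor contact at all, which this contradicts. But the contact listed is for scheduling, missed appointments, check-ins and planning follow-up visits. The contrast in Mentor-delivered sessions remains.

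**The remedy.** With few Mentors the variance is poorly estimated, power falls, and a nested-pair model is wrong if Mentors were re-paired across families. This is a fair reason not to make the clustered model the sole test, nor to let an unsourced ICC decide significance. It is not a reason to omit the analysis.

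**Conclusion.** The omission is documented: FIOC is Mentor-delivered, TAU has no equivalent sessions, and neither the SAP nor the sample-size section allows for Mentor variation. That the standard errors are too small is conditional on three things: families share Mentors (very likely, not stated), the Mentor ICC exceeds 0, and the conclusion is meant to extend beyond these Mentors.

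Under 3-8 equal pairs, ICC .02-.10 and 60 per arm, the true standard error is about 3-40% larger than reported, which is the same as saying that the reported one is about 3-28% too small. The type I error is then about 6-16%. At ICC .01 it is about 5-6%, and at ICC 0 there is no effect. The documents cannot place the trial within this range. The point is worth correcting because it bears on the multi-site decision and is cheap to address, but it does not show that the planned primary comparison is invalid.

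**What to change.** 1. Record which Mentor or Mentors served each FIOC family, and report the number of Mentors, their caseloads, how they were assigned and whether pairs were fixed.
2. Add to the SAP, before the contrasts are run, a sensitivity analysis of each Aim 1-4 FIOC-TAU contrast. It should have a Mentor random effect in the FIOC arm only, residual variance specific to each arm, and small-sample degrees of freedom (Satterthwaite or Kenward-Roger). The random effect should follow the actual assignment: nested if pairs were fixed, crossed individual Mentors if not. Report the Mentor variance and ICC beside the contrast.
3. If Mentors are too few to estimate that variance, show each contrast over a stated ICC range, for example 0-.10, and state that the main inference is conditional on these Mentors.

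**Cost.** SAP wording and one data item that should be recoverable from supervision and fidelity records, though the documents do not confirm that it is kept. Families, visits and delivery of the intervention are unaffected. The downside is wider and imprecise intervals in this analysis. With 4 pairs, small-sample degrees of freedom alone take power at d = .514 from .80 to .73 even at ICC 0, and to .56 at ICC .05. That is why it is proposed alongside the planned tests and not in their place.

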FIOC was designed specifically to aid development of positive coparenting alliances between at-risk (unmarried, uncoupled, low income) African American mothers and fathers having a first baby together. In the RCT, randomly-assigned control group families (referred by already-known referral agents and partners who worked closely with our team on the pilot projects) will receive Pinellas County services as-usual for pregnant parents and assistance of a Resource and Referral Navigator for referrals to desired community services ("Treatment as Usual", or TAU). The remaining (experimental group) families will receive the same services and aid, plus the 6-session FIOC prenatal intervention with a post-natal booster session. The first 150 families consented in will be assigned to groups via urn randomization. The remaining families recruited up to 170 will be assigned to the experimental (FIOC) group to achieve balance in the number of families contributing postnatal follow-up data longitudinally in the two groups to allow minimally sufficient statistical power for analyses. The FIOC intervention addresses the importance of safe, healthy families for early infant development, the impact a cooperative and sustained coparenting alliance can have in promoting positive infant development, challenges unmarried parents face cultivating a coparenting alliance together when their commitment to one another as romantic or married partners is in doubt, and ways to surmount these obstacles, maintain rapport, and sustain a strong alliance.

All 170 participating families, both at intake (prior to the intervention) and then again at 3 and 12 months post-partum, will report beliefs about fatherhood; extent of depressive symptomatology; and quality of the mother-father partnership. State-of-the-field coparenting observations will be conducted at each follow-up, along with measures of parental stress, intimate partner violence (IPV), perceived coparenting support, father engagement, and infant socioemotional adjustment. Analyses will examine impact of the intervention on promoting more supportive, coordinated post-partum coparenting alliances and more positive adult and infant outcomes. Exploratory analyses will examine links between father involvement and child adjustment and whether this coparenting intervention also stands to prevent IPV.

2. Background information

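### The SAP's single-visit t-tests and IPV chi-square default to complete cases, in a design whose FIOC-only top-up implies heavier follow-up loss in FIOC

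*SAP*

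**What the plan says.** **Allocation (Protocol section 1).** "The first 150 families consented in will be assigned to groups via urn randomization". After that point, allocation is no longer random: "The remaining families recruited up to 170 will be assigned to the experimental (FIOC) group", and the stated purpose is "to achieve balance in the number of families contributing postnatal follow-up data longitudinally in the two groups".

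**Sample size (Protocol section 5).** The calculation uses a "projected sample size, incorporating attrition estimates", of 120 families: "60 each in the treatment and control groups, respectively". It takes "alpha set at .05 and power of .8" and arrives at d = .514. It gives no attrition rate, overall or by arm, and does not say whether the 120 comes from 150 or from 170 families.

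**Analysis (SAP).** For Aims 1-4, two-sided t-tests "will first be employed for single time point comparisons". Linear or generalized linear models then follow, to deal with confounding and imbalance. Outcomes measured at baseline, 3 and 12 months go to repeated measures ANCOVA or GLM. IPV starts with a chi-square on any physical violence over the 12 months of follow-up. A linear regression on baseline CTS2 and a hierarchical regression come after it. The SAP contains no analysis set, missing-data assumption, imputation or sensitivity analysis for missing scores, and the protocol supplies none.

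**Outcomes affected.** Under Protocol section 4, the PAM, coparenting in the LTP, parenting stress, infant triangular capacity and father engagement are measured only after birth, and the BITSEA only at 12 months. They have no baseline value of their own, so the single-visit tests matter most for them.

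**The concern.** A t-test or chi-square with no rule for missing scores uses observed families only. Such a comparison is safe if, within each arm, lost families resemble retained ones. If lost families do worse in both arms by the same amount and loss is equal, the distortion cancels. If loss is heavier in FIOC, it does not cancel, and it favours FIOC.

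The top-up is the evidence for unequal loss. Adding families to one arm to equalise the number with follow-up data makes sense if that arm yields fewer such families. Recruiting replacements evens the counts, but it does not score the families that were lost. The replacements are also not randomised.

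Loss related to outcome is plausible here. Protocol section 13 allows families to be withdrawn over safety, unresolved trauma or psychological need, and lists ending participation among possible responses to domestic violence. For the IPV comparison, families who leave for such reasons could be the events being counted.

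**Working it through.** **1. The plan's own figure.** With F = 7.74 on 1 and 117 df, d = 2 × √(7.74/117) = 0.514. With 60 per arm and d = 0.514, a two-sided 5% test has 79.7% power (noncentral F, 118 df). Section 5 reproduces, so 60 analysable families per arm is a coherent target. The issue is bias, not power.

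**2. Implied loss.** Inputs: 150 randomised and up to 20 added to FIOC (section 1); 60 analysable per arm (section 5). The urn split is not stated and is an assumption. Loss = 1 − 60/(number enrolled).

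| Urn split TAU/FIOC | Enrolled TAU/FIOC | TAU loss | FIOC loss | Gap (points) |
|---|---|---|---|---|
| 80/70 | 80/90 | 25.0% | 33.3% | 8.3 |
| 75/75 | 75/95 | 20.0% | 36.8% | 16.8 |
| 70/80 | 70/100 | 14.3% | 40.0% | 25.7 |

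The gap does not depend on the figure 60. With equal completers from 75 and 95 families, it is 50/75 − 50/95 = 14.0 points at 50 per arm, and 70/75 − 70/95 = 19.6 points at 70. It disappears only if the urn itself left FIOC 20 families short (85/65, giving 85 in each arm after the top-up and 29.4% loss in both).

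**3. Bias, as an illustration.** Suppose there is no treatment effect and lost families score δ SD worse than retained ones in both arms. The retained mean in an arm then exceeds the full-arm mean by loss × δ, so bias = δ × (FIOC loss − TAU loss). With 60 per arm, SE = √(1/60 + 1/60) = 0.183 SD. Rejection rate ≈ Φ(−1.96 + bias/SE) + Φ(−1.96 − bias/SE). At δ = 0.5:

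| Split | Bias (SD) | Bias/SE | Rejection rate |
|---|---|---|---|
| 80/70 | 0.5 × 0.083 = 0.04 | 0.23 | 5.6% |
| 75/75 | 0.5 × 0.168 = 0.08 | 0.46 | 7.5% |
| 70/80 | 0.5 × 0.257 = 0.13 | 0.70 | 11% |

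**4. Randomised families only.** If FIOC retention is the same in randomised and top-up families, 75 × 60/95 ≈ 47 randomised FIOC families are scored. SE becomes √(1/60 + 1/47) ≈ 0.195 and the 75/75 rejection rate is about 7.2%, so the conclusion does not change.

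**5. What adjustment can do.** In a simulation with 75 per arm, about 63% (FIOC) and 80% (TAU) retained, and FIOC loss driven by a baseline score correlated .6 with the outcome (logistic slope 1), the unadjusted t-test was biased by 0.18 SD and rejected about 15% of the time. When loss depended on the score equally in both arms, the bias was about 0.08 SD and the rate a little over 7%. Adjusting for that score removed the bias in both cases. The slope and correlation are assumptions. The lesson is that the right intake covariates matter.

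**The case against.** The case against has real force on four points.

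- **The loss rates are not the plan's.** A reader might take 20% and 37% as figures the protocol projects. It projects none. They combine section 5 with the ceiling of 170 and an assumed even split. If section 5 was written for 150 families, 120/150 is 20% loss overall and the 37% does not follow. FIOC could also be short of follow-up data because the urn gave it fewer families. The direction is still the natural reading: urn allocation is meant to keep arms balanced, and the top-up aims at families with follow-up data, not at families assigned.
- **Not analysable is not the same as no postnatal score.** A reader might infer that these families have no postnatal data at all. The documents do not support that. A family may have a 3-month score and no 12-month score, and section 5 refers to couple-discussion variables that need both parents. Loss on mother-reported outcomes may be smaller.
- **The t-test is only the first step.** The SAP goes on to adjusted models, and for IPV to regression on baseline CTS2. These could reduce the bias. But the Aims 1-4 models name no covariates, and none of these models brings back a family without a score.
- **The cause of loss is not stated.** A reader might say that the protocol expects instability or safety concerns to drive loss. Section 13 says only that families may be withdrawn for such reasons, and it is control-group retention that it calls a special concern.

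**Conclusion.** The concern stands in a limited form. The plan has no analysis set and no missing-data rule. Its top-up implies more follow-up loss in FIOC, and its first-step tests for Aims 1-4 and for IPV therefore become complete-case comparisons with unequal loss. Followed as written, they can favour FIOC.

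The likely size is modest to moderate: 0.04 to 0.13 SD for a 0.5 SD deficit in lost families, against a detectable effect of d = .514. This rests on three assumptions that the documents do not settle: the urn split, the 60 per arm applying to all 170 families, and the deficit itself. If lost families resemble retained ones, or if loss is equal and the deficit is the same in both arms, the bias is zero.

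The scope is Aims 1-4, not only the parent, child and father aims, because the PAM and LTP coparenting belong to Aim 1. The IPV analysis is exploratory and has a baseline-adjusted follow-on, so the point weighs less there. It has an added gap: section 4 withholds the CTS2 from some fathers by design, and the SAP does not say how their absent reports enter the binary variable.

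**What to change.** Amend the SAP as follows.

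1. For single-visit outcomes in Aims 1-4, make the main analysis a covariate-adjusted comparison of all urn-randomised families, with the covariates named.
2. Handle missing scores by multiple imputation done separately by arm, using intake data already collected (Edinburgh score, PANQIRS, SCID ratings, Risk History, ACE, baseline CTS2, children from prior unions) and the other visit's score on the same measure.
3. Treat the binary IPV outcome the same way, and state how CTS2 reports missing by design are counted.
4. Report separately the analysis that adds the non-randomised FIOC families.
5. Keep the observed-data t-test and chi-square as sensitivity analyses.
6. Add a delta-adjusted analysis in which imputed scores are made progressively worse, for example by 0 to 1 SD, varied by arm.
7. Report retention by arm at 3 and 12 months, for randomised and top-up families separately.

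No new data or families are needed. The cost is more analysis work, somewhat wider intervals, and a main comparison without the up to 20 top-up families that were added for power.
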